13.3.2 Blood Phe Concentration

The observed value and change from Baseline in blood Phe will be summarized at each scheduled visit and across all visits. In addition, the average proportion of Phe values between the target range of 120 and 360 across each subject will be presented.

Another measurement of interest is the Index of Dietary Control (IDC), defined as half-year Phe level medians averaged over the first 6 months, over the first year, and annually thereafter. Descriptive statistics of the IDC will be produced.

Figures displaying mean change in Phe from baseline and IDC at each time point will be produced.

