4.1 Analysis Populations

The Full Analysis set (FAS) will consist of all subjects who enroll into the study.

The Enrolled population will consist of all subjects who enter Part 2 of the study and met the inclusion/exclusion criteria per CRF. This population involves subjects who respond to Kuvan and had a Bayley-III or IQ test score ≥ 80 within 6 weeks of determination of Kuvan responsiveness in Part 1. Kuvan responders consist of all subjects with at least 30% average reduction in blood Phe concentration calculated as the mean of the weekly percent change from baseline at Week 1, 2, 3 and 4 in Part 1.

The Efficacy population will consist of all subjects from the Enrolled population who have at least two WPSI/WISC assessments.

The Safety population will consist of all subjects who have received any study drug in the FAS population.

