4.5 Visit Window for Analysis

The baseline blood Phe concentration is defined as the mean of the screening and Week 0 (prior to dosing with Kuvan) result. Baseline measurement for other assessments is defined as the latest non-missing measurement prior to the first study drug administration in Part 1. If there are two or more measurements within an analysis visit window, the measurement that is closest to the scheduled time point will be used for analyses. If the two closest measurements to the scheduled time point are equidistant from that scheduled analysis time point, the average (or more conservative) of the two assessments will be used for analyses.

Table 4.5.1 presented below defines visit windows for the scheduled analysis time points by analysis parameter.

	SAP PKU-015, Version 3.0	Page 13 of 31
---	--------------------------	---------------

Table 4.5.1: Visit Windows

Assessment	Scheduled Time Point	Visit Window
Bayley-III	Baseline	First measurement date after determination of Kuvan responsiveness (Day 30 to Day 120)
	Month 6	Day 121 to Day 273
	Month 12	Day 274 to Day 456
	Month 18	Day 457 to Day 638
	Month 24	Day 639 to Day 821
WPPSI-III, WISC-IV (based on Month 2 occurrence)	Baseline	First measurement date after determination of Kuvan responsiveness at Month 2 visit (Day 30 to Day 120)
	Month 12	Day 121 to Day 548
	Month 24	Day 549 to Day 913
	Month 12 *i , where $i=2,3,4,5,6,7,\dots$	Day $365*i - 181$, Day $365*i + 183$
WPPSI-III, WISC-IV (based on first assessment)	Baseline*	First measurement date after determination of Kuvan responsiveness
	Month 12	Day 2 to Day 548
	Month 24	Day 549 to Day 913
	Month 12 *i , where $i=2,3,4,5,6,7,\dots$	Day $365*i - 181$, Day $365*i + 183$
Height, head circumference, physical exam	Baseline	Last measurement date prior to the initial study drug administration
	Week 4	Day 2 to 76
	Month 3	Day 77 to Day 137
	Month 6	Day 138 to Day 273
	Month 12	Day 274 to Day 456

	SAP PKU-015, Version 3.0	Page 14 of 31
---	--------------------------	---------------

Assessment	Scheduled Time Point	Visit Window
	Month 18	Day 457 to Day 638
	Month 24	Day 639 to Day 821
	Month 6*i, where i=2,3,4,5,6,7,...	Day $\text{round}(182*i + i/2) - 91$, Day $\text{round}(182*i + i/2) + 91 - \text{mod}(i,2)^*$
Tryptophan, tyrosine	Baseline	Last measurement date prior to the initial study drug administration
	Week 4	Day 2 to 76
	Month 3	Day 77 to Day 137
	Month 6	Day 138 to Day 273
	Month 12	Day 274 to Day 548

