	Month 24	Day 549 to Day 913
	Month 12*i, where i=2,3,4,5,6,7,...	Day $365*i - 181$, Day $365*i + 183$
	Blood Phe level, Dietary Phe, Weight, Vital Signs	Baseline
Week 1		Day 2 to Day 11
Week 2		Day 12 to Day 18
Week 3		Day 19 to Day 25
Week 4		Day 26 to Day 42
Month 2		First measurement date after determination of Kuvan responsiveness (Day 43 to Day 76)
Month 3		Day 77 to Day 106
Month 4		Day 107 to Day 137
Month 5		Day 138 to Day 167
Month 6		Day 168 to Day 273

	SAP PKU-015, Version 3.0	Page 15 of 31
---	--------------------------	---------------

Assessment	Scheduled Time Point	Visit Window
	Month 12	Day 274 to Day 456
	Month 18	Day 457 to Day 638
	Month 6*i, where i=2,3,4,5,6,7,...	Day $\text{round}(182*i + i/2) - 91$, Day $\text{round}(182*i + i/2) + 91 - \text{mod}(i,2)^*$
Additional Week 0 Vital signs	15 min postdose	1 min to 22 min elapsed time
	30 min postdose	23 min to 37 min elapsed time
	45 min postdose	38 min to 52 min elapsed time
	60 min postdose	53 min to 75 min elapsed time
	90 min postdose	76 min to 105 min elapsed time
	120 min postdose	106 min to 150 min elapsed time
	180 min postdose	151 min to 360 min elapsed time
Clinical laboratory tests	Baseline	Last measurement date prior to the initial study drug administration
	Week 1	Day 2 to Day 15
	Week 3	Day 16 to Day 25
	Week 4	Day 26 to Day 42
	Month 2	First measurement date after determination of Kuvan responsiveness (Day 43 to Day 76)
	Month 3	Day 77 to Day 106
	Month 4	Day 107 to Day 137
	Month 5	Day 138 to Day 167
	Month 6	Day 168 to Day 273
	Month 12	Day 274 to Day 456
	Month 18	Day 457 to Day 638
	Month 6*i, where i=2,3,4,5,6,7,...	Day $\text{round}(182*i + i/2) - 91$, Day $\text{round}(182*i + i/2) + 91 - \text{mod}(i,2)^*$

*Baseline refers to first assessment for this visit windowing

	SAP PKU-015, Version 3.0	Page 16 of 31
---	--------------------------	---------------

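### Two blood Phe summaries in SAP 13.3.2 have no period restriction or time structure, so they over-represent the first 6 months and reuse the responder-selection values without saying so.

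*SAP*

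**What the plan says.** Section 13.3.2 plans several descriptive outputs for blood Phe. Two of them collapse the whole study into one figure:

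- "The observed value and change from Baseline in blood Phe will be summarized at each scheduled visit and across all visits"; the concern is the summary over all visits, not the by-visit one.
- "the average proportion of Phe values between the target range of 120 and 360 across each subject will be presented".

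No period, weighting or exclusion of Part 1 is given for either. The same section defines the Index of Dietary Control (IDC), which does have a time structure: "defined as half-year Phe level medians averaged over the first 6 months, over the first year, and annually thereafter".

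Table 4.5.1 (Section 4.5) sets the blood Phe windows. Part 1 has Weeks 1, 2, 3 and 4, the last covering "Day 26 to Day 42". Months 2, 3, 4, 5 and 6 follow, the last covering "Day 168 to Day 273". After that there is one window per half-year ("Month 6*i, where i=2,3,4,5,6,7" and so on). Within a window, "the measurement that is closest to the scheduled time point will be used for analyses".

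Section 4.1 says: "Kuvan responders consist of all subjects with at least 30% average reduction in blood Phe concentration", taken over Weeks 1-4 of Part 1. Section 13 uses the Efficacy population unless stated otherwise, and that population is drawn from these responders.

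**The concern.** Blood Phe is sampled densely at the start and sparsely afterwards. A summary over all values then describes the sampling schedule as much as the child's long-term exposure. Two separate problems follow.

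First, the early months carry far more weight than their share of follow-up. That share also differs between children, because it rises as follow-up shortens.

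Second, the four Part 1 values are the ones that admitted the child to the analysed population. Their mean change is at least a 30% fall by definition. Using them again inside an overall change from baseline, without a label, puts selection into a figure that will be read as evidence of control over years.

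Part 1 also ran under a narrower dietary instruction than the rest of the study. Section 3.2 asks for current dietary Phe intake to continue in Part 1, with an optional increase at low Phe. The general design also allows a decrease at high Phe. Pooling mixes the two conditions.

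At stake is the interpretation of two descriptive results, not the study's conclusion on IQ.

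**Working it through.** The plan states no figure for this point, so there is none to reproduce. The check counts values against time.

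**Inputs.** From Table 4.5.1, one value per window: Weeks 1-4 give 4, Months 2-6 give 5, and Months 12 to 84 in half-year steps give 13. From Section 3.2: planned treatment of 7 years (84 months). Assumed: every value counts equally, and no additional samples enter.

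**Share of values against share of time.** Total to Month 84 = 4 + 5 + 13 = 22.

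| Follow-up (months) | First 6 months, values | Share of values | Share of time | Weeks 1-4, share of values |
|---|---|---|---|---|
| 12 | 9/10 | 90% | 50% | 40% |
| 36 | 9/14 | 64% | 17% | 29% |
| 60 | 9/18 | 50% | 10% | 22% |
| 84 | 9/22 | 41% | 7% | 18% |

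At 84 months the over-representation is 40.9/7.1, about six-fold. Weeks 1-4 cover 28 days of 84 × 30.4375 = 2,557 days, or 1.1% of the time. If the pre-dose baseline is also counted as a visit, which the SAP leaves open, the early post-baseline share is 9/23 = 39%.

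**Reduction guaranteed by selection.** Let B be a child's baseline. All four weekly percent changes share this denominator, so a mean percent change of -30% or lower is the same as a mean absolute change of -0.30 × B or lower. The argument therefore holds in either unit. Suppose Phe returned exactly to baseline from Month 2 onward:

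- 7 years, equal counting: 4/22 × 30 = at least a 5.5% reduction reported.
- 3 years, equal counting: 4/14 × 30 = at least 8.6%.
- 7 years, weighted by time: 1.1% × 30 = about 0.3%.

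This assumes that the windowed values are those used for the responder rule and that the child did not enter by exemption.

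**In-range proportion.** Let e be the in-range rate in the first 6 months and l the later rate. At 84 months the equal-count result minus the time-weighted result is (9/22 - 6/84) × (e - l) = 0.338 × (e - l). The rates below are assumptions:

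- e = 90%, l = 60%: (9 × 0.9 + 13 × 0.6)/22 = 72.3%, against (6 × 0.9 + 78 × 0.6)/84 = 62.1%.
- e = 80%, l = 70%: 74.1% against 70.7%.
- e = l: no difference.
- e = 60%, l = 90%: (9 × 0.6 + 13 × 0.9)/22 = 77.7%, against (6 × 0.6 + 78 × 0.9)/84 = 87.9%.

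The sign follows e - l, which the SAP does not give.

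**Effect of possible changes.** Dropping Weeks 1-4 alone leaves 5/18 = 28% of values in Months 2-6. Taking the mean of half-year values gives the first half-year 1/14 = 7.1%, which equals its share of time.

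**The case against.** A good deal can be said for the plan as written.

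- **The long-term course is shown elsewhere.** By-visit summaries, figures of mean change and the IDC, which reports later years annually, would all reveal a loss of control. This stands for Phe level. It does not cover the in-range proportion, which is planned only as one overall figure.
- **Equal counting is not written.** The SAP is silent on weighting. With one value kept per window, equal counting is the natural reading, but it remains an inference.
- **The number of values may differ.** The in-range statistic refers to values, not visits, and Table 4.5.1 sets analysis windows rather than sampling frequency. A half-year median hints at more than one sample per half-year. Additional later samples would lower the early share. This stands, and the 22-value count is conditional on it.
- **Selection does not imply in-range values.** The rule requires a fall, and values below 120 count as out of range. Section 3.2 foresees that some children may fall that low in Part 1. So the early weight could lower the proportion.
- **Very early leavers are largely excluded.** The Efficacy population needs two WPPSI/WISC assessments, which are scheduled at intervals of one or two years.

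A reader might go further and infer that early values dominate the 7-year result. They do not: 13 of 22 scheduled values fall after Month 6, and early values are a majority only when follow-up is under 60 months. A reader might also infer that durable control will be overstated. That needs an assumption about how Phe changes over time, and the document provides none.

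**Conclusion.** The point holds in a limited form. On the SAP's own windows, with equal counting and no additional samples, the first 6 months carry 41% of a 7-year completer's values in 7% of the time (64% in 17% at 3 years). The selection values carry 18% in about 1%.

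The firm part is the pooled change from baseline. It includes a contribution fixed by selection, at least 5.5% of baseline at 7 years and 8.6% at 3 years, whatever happens after Week 4. The in-range proportion is tilted toward the early period by an unknown amount and in an unknown direction, with no planned output that would expose it.

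Only these two exploratory, descriptive statistics are affected. The primary analysis of FSIQ and its success rule do not depend on them. The change is worth making because it is cheap and the two figures are likely to be quoted as overall summaries of Phe control.

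**What to change.** In Section 13.3.2:

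1. Compute both statistics per subject from on-treatment values after Week 4, either by year or as the mean of half-year values (the structure that the IDC already uses), and then average over subjects.
2. Report Weeks 1-4 separately, labelled as the responder-selection period.
3. State that pre-dose values are excluded, and whether samples beyond the one kept per window are used.

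Removing Part 1 without the yearly or half-year structure is not enough, given the 28% that would remain in Months 2-6.

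The cost is SAP wording and slightly more programming, with no new data. The reported Phe reduction may look less favourable.

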3.2 Study Design

This 2-part, multicenter, open-label study is designed to evaluate the safety of Kuvan and its effect on neurocognitive function, blood Phe concentration, and growth in children with PKU when treatment is initiated at 0-6 years of age. The study will be considered complete when approximately 45 subjects have completed 7 years of treatment.

One of the goals of the study will be to decrease blood Phe levels to reach a goal of ≤ 240 $\mu\text{mol/L}$. Subjects will meet with a dietician at each study visit to review dietary Phe intake. Dietary Phe may be added to the diet, at the discretion of the Investigator, if a blood Phe level falls below 120 $\mu\text{mol/L}$ or decreased if blood Phe level is above 240 $\mu\text{mol/L}$. If a subject's blood Phe falls below 120 $\mu\text{mol/L}$, at the discretion of the investigator, a gradual increase of approximately 5-20 mg/kg of Phe supplement may be added to the diet. If a subject's blood Phe level goes above 240 $\mu\text{mol/L}$, dietary Phe may be decreased by

	SAP PKU-015, Version 3.0	Page 7 of 31
---	--------------------------	--------------

approximately 5 to 20 mg/kg or defined by the standard used at each treatment center, at the discretion of the investigator.

Part 1: Evaluation of Kuvan Responsiveness

Beginning at Week 0 and after all baseline assessments are completed, subjects enrolled into the study will receive 20 mg/kg Kuvan daily for 4 weeks. Subjects will return to the clinic weekly for safety assessments and blood Phe concentration measurement. Subjects should continue with their current amount of dietary Phe intake. However, if a subject's blood Phe concentration drops below 120 $\mu\text{mol/L}$, at the discretion of the Investigator, a gradual increase by approximately 5 to 20 mg/kg of daily dietary Phe supplement may be added to the diet. It is important to avoid unstable swings in blood Phe concentrations. No dose adjustments can be made during Part 1 without consultation with the Medical Monitor.

Part 2: Neurocognitive Study

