3.3 Study Population

Individuals eligible to participate in this study must meet all of the following criteria:

- Parent(s) or guardian(s) willing and able to provide written, signed informed consent after the nature of the study has been explained, and prior to any research-related procedures.
- Parent(s) or guardian(s) willing and able to comply with all study procedures.
- Female subjects of childbearing potential (as determined by the investigator) and sexually mature male subjects willing to use a medically accepted method of contraception throughout the study. Female subjects of childbearing potential willing to undergo periodic pregnancy tests during the course of the study
- Established diagnosis of PKU with hyperphenylalaninemia (HPA) documented in the medical record by at least 2 blood Phe concentrations $\geq 360 \mu\text{mol/L}$ (6 mg/dL) taken at least 3 days apart
- Documented blood Phe control (defined by the standard used at each treatment center) prior to study enrollment, if applicable (eg, the subject is old enough for these data to be collected); blood Phe concentrations for subjects < 6 months old at Screening must be considered controlled and stable by the Investigator

	SAP PKU-015, Version 3.0	Page 9 of 31
---	--------------------------	--------------

- Willing to adhere to a prescribed Phe-restricted diet in order to maintain blood Phe concentrations within the recommended ranges established at the subject's study site
- Age 0 to 6 years, inclusive, at Screening

Individuals eligible to participate in Part 2: Neurocognitive Study must meet **all** of the following criteria:

- Completion of Week 4 visit in Part 1
- Responsive to Kuvan during Part 1, defined as a $\geq 30\%$ average reduction in blood Phe concentration calculated as the mean of the weekly percent change from baseline in blood Phe concentration at Weeks 1, 2, 3, and 4
- Bayley-III or IQ test score ≥ 80 when tested within 6 weeks of determination of Kuvan responsiveness in Kuvan-responsive subjects

Individuals who meet any of the following exclusion criteria will not be eligible to participate in the study:

- Has known hypersensitivity to Kuvan or its excipients
- Use of Kuvan or any investigational product or investigational medical device within 30 days prior to screening, or requirement for any investigational agent prior to completion of all scheduled study assessments

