13.3 Exploratory analyses

Exploratory variables include:

- IQ scores
- Blood Phe concentration
- Relationship between neurocognitive testing and blood Phe
- Prescribed dietary Phe

A subject listing of IQ scores, neurocognitive testing results, blood Phe, and prescribed dietary Phe will be provided.

	SAP PKU-015, Version 3.0	Page 23 of 31
---	--------------------------	---------------

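### SAP Section 13.3.2 calls 120–360 the target range for blood Phe, but Section 3.2 sets a goal of ≤ 240 µmol/L and no planned proportion is scored against 240

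*SAP*

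**What the plan says.** Section 3.2 (Study Design) gives the treatment aim: "One of the goals of the study will be to decrease blood Phe levels to reach a goal of ≤ 240" µmol/L. It then says when diet may be changed. At the low end, "Dietary Phe may be added to the diet, at the discretion of the Investigator, if a blood Phe level falls below 120" µmol/L. At the high end, dietary Phe may be added to or "or decreased if blood Phe level is above 240" µmol/L. Both changes are at the investigator's discretion.

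Section 13.3.2 (Blood Phe Concentration) plans the analysis: "The observed value and change from Baseline in blood Phe will be summarized at each scheduled visit and across all visits". It adds one measure of control against fixed limits: "the average proportion of Phe values between the target range of 120 and 360 across each subject will be presented". It gives no unit and no source for the upper limit. The Index of Dietary Control (IDC) is also summarised there, as averaged half-year medians.

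Section 3.3 (Study Population) touches the subject twice. PKU must be "documented in the medical record by at least 2 blood Phe concentrations" of at least 360 µmol/L, which is a diagnostic threshold. Families must also accept a Phe-restricted diet "in order to maintain blood Phe concentrations within the recommended ranges established at the" subject's study site; the SAP gives no numbers for those ranges.

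Section 13.3 lists blood Phe among the items under "Exploratory variables include".

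**The concern.** The two sections use different upper limits for what reads as the same thing. A value of 300 µmol/L misses the Section 3.2 goal and permits a cut in dietary Phe, yet Section 13.3.2 counts it as in target. The word target is what makes this a contradiction rather than a free choice of descriptive band.

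The in-range proportion is the only planned summary that scores Phe control against fixed limits. Sections 3 and 3.2 name the effect on blood Phe among the things the study is designed to evaluate, and Section 13.3.1 presents the 7-year FSIQ analysis as an assessment of Phe control with Kuvan. A reader who wants to know how well Phe was controlled will turn to this proportion and may take it as attainment of the study's own goal. It does not measure that.

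**Working it through.** The plan has no figure of its own to reproduce here. The check compares the texts and then illustrates the possible size.

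**Step 1: every Phe limit in the SAP.**

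| Section | Limit (µmol/L) | Role |
|---|---|---|
| 3.2 | ≤ 240 | stated study goal |
| 3.2 | < 120 | dietary Phe may be added |
| 3.2 | > 240 | dietary Phe may be reduced |
| 3.3 | ≥ 360, at least twice | diagnosis at entry |
| 3.3 | site ranges, no numbers | diet requirement |
| 13.3.2 | 120 to 360, no unit | target range for the proportion |

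Nothing defines 360 as a treatment target, and nothing links the site ranges to 13.3.2. The range scored is 360 − 120 = 240 units wide. The band implied by the two diet limits is 240 − 120 = 120 units wide. The upper half of the scored range therefore lies above the study goal.

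**Step 2: is attainment of 240 reported elsewhere?** Section 13.3.2 plans observed values, change from baseline, the one proportion and the IDC. Section 13.3.3 plans correlations, using observed Phe, its change and its SD. None is a proportion of values ≤ 240 or within 120–240.

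**Step 3: possible size.** The SAP gives no on-treatment mean, SD or shape. The distributions below are assumptions, chosen to cover well-controlled and less well-controlled Phe. For a normal distribution with mean μ and SD σ, the share between a and b is Φ((b − μ)/σ) − Φ((a − μ)/σ). For μ = 240 and σ = 100, the share in 120–360 is Φ(1.2) − Φ(−1.2) = 0.770, and the share in 120–240 is Φ(0) − Φ(−1.2) = 0.385.

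| Mean, SD | 120–360 | 120–240 | ≤ 240 | >240–360 | <120 | Ratio to 120–240 | Ratio to ≤ 240 |
|---|---|---|---|---|---|---|---|
| 240, 100 | 0.770 | 0.385 | 0.500 | 0.385 | 0.115 | 2.00 | 1.54 |
| 300, 100 | 0.690 | 0.238 | 0.274 | 0.451 | 0.036 | 2.89 | 2.52 |
| 200, 75 | 0.840 | 0.560 | 0.703 | 0.280 | 0.143 | 1.50 | 1.20 |
| 150, 75 | 0.653 | 0.540 | 0.885 | 0.113 | 0.345 | 1.21 | 0.74 |

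Each ratio is the 120–360 share divided by the share named. The difference between the reported share and the ≤ 240 share equals the share above 240 to 360 minus the share below 120. For mean 240, SD 100 that is 0.385 − 0.115 = +0.270. For mean 150, SD 75 it is 0.113 − 0.345 = −0.232. So the reported figure can overstate or understate attainment of ≤ 240, depending on how many values fall below 120.

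**Step 4: does the shape matter?** With lognormal Phe instead (assumed medians 180, 240 and 300; log-SD 0.3 and 0.5), the share in 120–360 is 61% to 90%, the share in 120–240 is 23% to 74%, and 16% to 50% of values lie above 240 and up to 360. The picture is the same.

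**The case against.** The case against has several good points. Section 3.2 calls ≤ 240 only one of the study's goals, diet changes are discretionary, and Section 3.3 refers to site ranges. A wider common range for describing control across sites could sit beside a tighter goal, and 13.3.2 does not claim to measure the 3.2 goal. That would be a sound defence if the SAP said so. It does not: it gives no source for 360 and calls the range the target.

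The band 120–240 is inferred from the two diet limits; the stated goal has no lower bound. This stands. The comparison with ≤ 240 is the one to rely on, and there the direction is not fixed, so nothing shows that the chosen range flatters the drug.

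The sizes rest on assumed distributions. They show how far the two measures can differ, not how far they will differ in this trial.

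The consequence is small. The proportion has no test or success rule and does not enter the primary FSIQ slope, the supportive analysis or the Section 13.3.3 correlations. Medians and quartiles by visit show whether half or three quarters of values are at or below 240, and the listings would let someone derive the missing share. This limits the harm, but quartiles do not give the average per-subject proportion, and a listing is not a planned summary.

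The missing unit is a detail: the other blood Phe limits are in µmol/L, so the meaning is clear.

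**Conclusion.** The concern holds. The SAP states a Phe goal of ≤ 240 µmol/L and then scores its only in-target proportion against 120–360 without reconciling the two. Under the assumed normal distributions, 11% to 45% of values would be labelled in target while missing the goal. The reported share would be 0.7 to 2.5 times the share ≤ 240, and 1.2 to 2.9 times the share in the inferred 120–240 band. The contradiction follows from the text alone; only the sizes depend on the assumptions.

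This is a mislabelled exploratory summary and a missing row, with no effect on the primary conclusion. It should be corrected, but it is not critical.

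The protocol was not available for this check and may explain 360. Section 3 of the SAP says that the SAP prevails where its analysis text and the protocol's differ, so the label needs correcting in the SAP itself.

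**What to change.** In Section 13.3.2, report the average per-subject proportion of Phe values ≤ 240 µmol/L and within 120–240 µmol/L beside the planned 120–360. A compact way is four bands (<120, 120–240, >240–360 and >360 µmol/L) plus a row for ≤ 240. State the unit. Then either call 120–360 a descriptive range rather than the target, or add one sentence saying where it comes from and why it differs from the Section 3.2 goal.

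The cost is a wording change and a few rows in one descriptive table, using data already collected. The planned 120–360 figure stays. The sponsor should accept that the share shown against the tighter limit may look less favourable.
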